11.3.1. Analysis Plans for Primary Objective

ORR will include confirmed complete response (CR) + confirmed partial response (PR) and will be assessed based on RECIST 1.1 criteria. ORR will be reported with the 95 % confidence interval (CI). Progression of any radiated tumors will be considered in this evaluation but response of radiated tumor(s) will not be considered as evidence of response for the purpose of this study unless all tumor sites are radiated.

11.3.2. Analysis Plans for Secondary Objectives

Treatment-related AE will be reported in tabular format, and AE rates, including the proportion of participants experiencing Grade 3+ treatment-related toxicities, will be reported with the 95 % CI.

PFS will be analyzed using the Kaplan-Meier method, and median PFS will be computed with the associated 95 % CI. Subjects who have not progressed and are still alive will be right-censored at the date of the last disease evaluation. Kaplan-Meier curves will be plotted.

OS will be analyzed using the Kaplan-Meier method, and median OS will be computed with the associated 95 % CI. Subjects who have not died will be right-censored at the date of the last follow-up, and Kaplan-Meier curves will be plotted.

Clinical benefit rate (defined as CR + PR + SD at \geq 6 months) will be reported via waterfall plot, and the 95 % CI for the clinical benefit rate will be computed.

Duration of response, duration of overall complete response and time to progression will be evaluated using the Kaplan-Meier method. Medians will be computed with the associated 95 % CI, and Kaplan-Meier curves will be plotted.

Patient-reported health-related quality of life will be evaluated using summary statistics and generalized linear mixed-effects models for measurements over time.

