1.3. Potential Risks and Benefits

1.3.1. *Potential Risks*

NKTR-214

The potential AEs of NKTR-214 have been assessed in recent clinical studies and commonly include: fatigue, flu-like symptoms, rash, fever, pruritus, hypotension, decreased appetite, arthralgia, and cough. Flu-like symptoms, rash and pruritus are assumed to be cytokine mediated and have occurred 3-4 days after treatment. These were mild to moderate in severity. Other possible risks include, anemia, periorbital edema, cerebrovascular accident, atrial fibrillation and tachycardia, abdominal pain, constipation, diarrhea, nausea, weight decrease, myalgia, dizziness, headache, syncope, anxiety, dyspnea, dysphonia, and pleural effusion.

SAEs of cerebrovascular accident (CVA), including one fatal event, have been observed in patients who have received NKTR 214 in the triplet combination with nivolumab and ipilimumab and in the doublet combination with nivolumab. A comprehensive search (data cutoff 21 June 2019) found 3 of 43 patients (7 %) who received triplet therapy in Study 16-214-02 (PIVOT-02) to have CVA events, all of which were considered by the investigator to be related to treatment with bempegaldesleukin, nivolumab, and ipilimumab. Additionally, 8 of 478 patients (1.7 %) who received doublet therapy (bempegaldesleukin and nivolumab) in Study 16-214-02 had CVA events, which were considered by the investigator to be related to treatment with bempegaldesleukin and nivolumab in 3 patients, to nivolumab in 1 patient, and unrelated to treatment in 4 patients. The relationship of these events to the triplet and doublet combinations is unclear. Based on these events and a comprehensive assessment of CVA across all NKTR-214 clinical studies, CVA has been escalated to an adverse event of special interest (AESI) and mitigations have been put in place to reduce the risk of CVA. These mitigations include implementation of a CVA AESI management algorithm (Appendix B) and updates to the exclusion criteria, renal function and hydration assessment, hydration guidelines, concomitant and prohibited medications, dose modification guidelines, and discontinuation criteria. Additional information on the clinical safety and risk of CVA is found in the NKTR-214 Investigator's Brochure (IB).

There is also the risk that previously unidentified AE could occur, as this is an investigational agent.

Anti- PD-1

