2.2. Secondary

Objective	Brief Description/Justification of Outcome Measure	Outcome Measured By	Time Frame
Evaluate the safety of NKTR-214 in combination with anti-PD-1 therapy and palliative radiation.	Grade 3 or grade 4 adverse event except those listed in 8.3.2 are anticipated to occur in < 25 % of patients based on the previous rate of 11 % with PD-1 inhibition and radiation. The safety of this combination must be established prior to evaluation of efficacy.	Toxicities \geq Grade 3 will be defined by the NCI Common Terminology Criteria for Adverse Events (CTCAE) v5. Toxicities not determined to be "unrelated" to treatment, will be considered treatment-related (including those that are unlikely, possibly, probably, or definitely related).	
 Study screening Cycle 1, day 1, 8 Cycle 2, day 1, 8 Cycle 3+, day 1 Every 4 months once off study without progression for 5 years, Every 6 months once off study with progression for 3 years

Objective	Brief Description/ Justification of Outcome Measure	Outcome Measured By	Time Frame
Determine CB, PFS, duration of response, and OS after treatment with NKTR-214, anti- PD-1, and palliative radiation.	PFS, OS, CB, and duration of response were chosen as efficacy outcomes based on prior immunotherapy trials. Duration of response is particularly important, as more durable responses are expected with immunotherapy.	
 CB will include confirmed complete response (CR) + confirmed partial response (PR) + stable disease at \geq 6 months (SD) and will be determined as per RECIST1.1. PFS is defined as the time from D1 of treatment until the criteria for disease progression is met as defined by RECIST1.1 or death as a result of any cause. OS is defined as time from D1 of treatment until death as a result of any cause. Duration of response is the period measured from the time that measurement criteria are met for complete or partial response (whichever status is recorded first) until the date that recurrent or progressive disease is objectively documented. 	
 D1 of treatment Standard-of-care imaging follow-up \sim3 and 6 months after Cycle 1 Time of disease progression Death

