8.1.4. Adverse Event of Special Interest (AESI)

Based on the results of prior studies, CVA has been defined as an AESI. Any CVA will be reported as an AESI.

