8.4.2. Serious Adverse Event Reporting

Depending on the nature, severity, and attribution of the serious adverse event an SAE report will be phoned in, submitted in writing, or both according to Table 1 below. All SAEs must also be reported to the UWCCC DSMC. All SAEs must also be reported to the UW IRB (if applicable), and any sponsor/funding agency not already included in the list.

Determine the reporting timeline for the SAE in question by using the following table.

Table 1: FDA Reporting Requirements.

Phase 1 and Early Phase 2 Studies: Expedited Reporting Requirements for Adverse Events that Occur on Studies under an IND/IDE within 30 Days of the Last Administration of the Investigational Agent/Intervention 1,2 FDA Reporting Requirements for Serious Adverse Events (21 CFR Part 312)

NOTE: Investigators **MUST** immediately report to the UWCCC DSMC, Nektar Therapeutics, and the IRB (if applicable) and any other parties outlined in the protocol ANY SAE, whether or not they are considered related to the investigational agent(s)/intervention (21 CFR 312.64).

An adverse event is considered serious if it results in ANY of the following outcomes:

- 1) Death.
- 2) A life-threatening adverse event (the subject was at risk of death at the time of the event; it does not refer to an event that hypothetically might have caused death if it were more severe).
- 3) An adverse event that results in inpatient hospitalization or prolongation of existing hospitalization for \geq 24 hours. *
- 4) A persistent or significant incapacity or substantial disruption of the ability to conduct normal life functions.
- 5) A congenital anomaly/birth defect.
- 6) Important Medical Events (IME) that may not result in death, be life threatening, or require hospitalization may be considered serious when, based upon medical judgment, they may jeopardize the subject and may require medical or surgical intervention to prevent one of the outcomes listed in this definition (FDA, 21 CFR 312.32; ICH E2A and ICH E6).

ALL SAE that meet the above criteria **MUST** be immediately reported to the UWCCC DSMC and Nektar within the timeframes detailed in the table below:

Hospitalization	Grade 1 and Grade 2 Timeframes	Grade 3-5 Timeframes
Resulting in hospitalization \geq 24 hours	10 Calendar Days	
Not resulting in Hospitalization \geq 24 hours	Not required	24 Hour; 5 Calendar Days

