For unexplained neurological symptoms (such as hemiparesis, confusion, dysarthria, or visual disturbances) that may be associated with CVA: **perform neurological imaging with MRI including diffusion-weighted imaging (DWI) as soon as feasible after initial presentation of symptoms (preferably within 24 hours)**. DWI MRI is preferred, but if contraindicated, alternative imaging modalities may be used.

If imaging is consistent with a CVA, proceed to the following:

1	
For any new CVA events confirmed by imaging (DWI MRI preferred unless contraindicated), regardless of neurological symptoms (e.g., cryptogenic CVA):
 
 • Discontinue study treatment for patients receiving NKTR-214 in combination with a checkpoint inhibitor 
For suspected TIA without clear alternative etiology:
 
 • Study treatment for patients receiving NKTR-214 in combination with a checkpoint inhibitor may be continued only after careful risk-benefit assessment by the Investigator
2	Obtain a neurology consultation
3	Perform laboratory assessments (Assessments include coagulation studies including D-dimer, complete blood count with differential, serum blood urea nitrogen, and creatinine. Additionally, collect an exploratory biomarker test if a baseline exploratory biomarker test was collected).
4	Consider cardiac echocardiogram (trans-esophageal as appropriate) to evaluate for potential source of emboli.

CVA = cerebrovascular accident; DWI = diffusion-weighted imaging; MRI = magnetic resonance imaging; TIA = transient ischemic attack.

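### Section 11.3.2 names an AE table for treatment-related events only and no CVA output, so a CVA rated unrelated would be in no named final-analysis table

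*Combined protocol and SAP*

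**What the plan says.** Section 1.3.1 explains why CVA was raised to an AESI. In PIVOT-02, 3 of 43 patients on a triplet (NKTR-214, nivolumab, ipilimumab) had a CVA, all rated related. On the NKTR-214 and nivolumab doublet, 8 of 478 (1.7%) had one. Investigators attributed 3 of those 8 to both drugs and the rest "to nivolumab in 1 patient, and unrelated to treatment in 4 patients. The relationship of these events to the triplet and doublet combinations is unclear".

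Section 8.1.4 lists CVA as the only AESI and sets one rule: "Any CVA will be reported as an AESI". It does not say in which output or on what timeline.

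The safety analysis is one sentence in 11.3.2: "Treatment-related AE will be reported in tabular format, and AE rates, including the proportion of participants experiencing Grade 3+ treatment-related toxicities, will be reported", with a 95% CI. The filter is defined in 2.2: "Toxicities not determined to be 'unrelated' to treatment, will be considered treatment-related". The same entry counts an event rated *unlikely* as related, so only *unrelated* events fall outside.

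Data capture is wider than the analysis. Section 8.1 puts every AE on the eCRF with its grade and relatedness. Section 8.2 collects AEs to 30 days after treatment, and SAEs to 90 days or the start of a new anti-cancer therapy. After 90 days it records only SAEs rated possibly, probably or definitely related.

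**The concern.** The attribution filter falls on the harm for which the plan itself calls the causal relationship unclear. With no control arm, the only way to judge the CVA rate of this regimen is to set it beside an outside figure. The outside figure in 1.3.1 (8/478) counts CVAs of every attribution, so a count of treatment-related CVAs alone is not comparable with it.

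The trial adds radiation to the drug combination and, on the strength of the PIVOT-02 toxicity results, forgoes a dose-escalation stage. The final report is then the main public evidence on CVA with this regimen. If 11.3.2 is followed to the letter, that report could show no CVA in its AE table when one had occurred.

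**Working it through.** **1. Tracing a CVA rated unrelated through section 11.**

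- *AE table:* "Treatment-related AE will be reported in tabular format". By 2.2, an *unrelated* event is not treatment-related, so it is out.
- *Named rate:* Grade 3+ treatment-related toxicities. It is out for the same reason.
- *Other outputs:* 11.3 and 11.3.1 to 11.3.4 name no AESI, CVA, SAE or all-cause AE table.
- *The term AE rates:* it carries no attribution limit of its own, and no CVA rate is specified under it. Whether it covers the event is undetermined.

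**2. Reproducing the plan's figures (1.3.1).**

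- Doublet: 8/478 = 1.67%, stated as 1.7%. Exact 95% CI 0.73% to 3.27%.
- Triplet: 3/43 = 6.98%, stated as 7%.
- Attributions: 3 + 1 + 4 = 8. Unrelated: 4/8 = 50%, exact 95% CI 16% to 84%.

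**3. Chance that the table loses a CVA.** This assumes that the doublet rate and split apply to the 24 participants of section 11.2.

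- Rate of *unrelated* CVA: 4/478 = 0.84%. Expected number: 24 × 0.00837 = 0.20.
- P(at least one) = 1 − (1 − 0.00837)^24 = 18%.
- Range over the CI of the all-cause rate, with the split held at one half: 0.73%/2 = 0.36% gives 8%; 3.27%/2 = 1.64% gives 33%.
- Range over the CI of the split, with the rate held at 1.67%: 0.0167 × 0.157 = 0.0026 gives 1 − (1 − 0.0026)^24 = 6%; 0.0167 × 0.843 = 0.0141 gives 29%.

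Neither range carries both uncertainties at once, so each is somewhat too narrow.

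**4. Effect of one such event (exact 95% CI).**

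- Counted: 1/24 = 4.2%, CI 0.1% to 21.1%.
- Not counted: 0/24, CI 0% to 1 − 0.025^(1/24) = 14.2%.

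**5. The reporting rules for CVA, side by side.**

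- 8.1.4: any CVA is reported as an AESI.
- 8.4.2, Table 1: no AESI row. A Grade 1–2 event without a hospital stay of at least 24 hours falls in a cell marked not required.
- 8.2: after 90 days, an SAE rated *unrelated* or *unlikely* is not recorded at all.
- 14.5: any SAE goes to the supplier within 24 hours, with no exception by grade or hospital stay.

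**The case against.** The strongest reply is that the plan contains no rule excluding unrelated events. It promises that "AE rates, including the proportion of participants experiencing Grade 3+ treatment-related toxicities, will be reported with the 95 % CI", and the treatment-related proportion is only one example within that phrase. This stands: for rates, the problem is ambiguity. It does not supply a CVA rate, and it does not widen the one named table.

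A reader might infer that an unrelated CVA would go unnoticed. The documents do not support that. Section 8.4.2 requires any SAE to be reported whatever its attribution, 9.1.1 gives the DSMC cumulative SAEs and toxicities each quarter, and 14.5 sends every SAE to the supplier. These are monitoring routes, however, and do not replace a final-analysis output.

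A reader might also infer that related but low-grade CVAs are lost, such as the imaging-detected events that Appendix B covers. They are not, because the treatment-related table has no grade limit.

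Nor is Table 1 plainly in conflict with 8.1.4. The table governs expedited reporting of SAEs, and 8.1.4 does not say expedited. What is missing is a stated route and timeline for an AESI that is not serious or is low grade.

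Finally, the prior split may not transfer. Section 1.3.1 does not give the earlier study's attribution scale. If it was two-level, some events called unrelated there might be rated *unlikely* here and so be tabulated. This trial also excludes patients with a prior CVA or TIA, and 1.3.1 lists further mitigations. Both points stand as limits on the 18%.

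**Conclusion.** The point holds as a gap in the final analysis. Section 11 names one AE table, filtered on attribution, and no CVA output, so a CVA rated *unrelated* is in no named table and may or may not be covered by the term AE rates.

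The chance that this affects at least one event is about 18% (8% to 33%), on the assumption that the prior doublet rate and attribution split apply. The larger figures that a reader might reach for do not measure this gap. The 33% obtained as 1 − (1 − 8/478)^24 is the chance of any CVA, including those the table would show. The triplet rate of 7% comes from a regimen with ipilimumab, which is not given here.

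Sample size, primary endpoint and DSMC oversight of serious events are unaffected.

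**What to change.** In 11.3.2:

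- State that all CVAs will be tabulated regardless of attribution and grade, in all participants who received at least one dose of NKTR-214, with the proportion and an exact 95% CI. Naming the population matters because the Protocol Summary places safety in the efficacy-evaluable population.
- State the collection window, given the 30-day and 90-day limits in 8.2.
- Show all-cause Grade 3+ AEs beside the treatment-related rate.
- Say whether the term AE rates means all-cause, treatment-related or both.

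Separately, reconcile 8.1.4, Table 1 in 8.4.2, the 90-day rule in 8.2 and the supplier rule in 14.5, so that the route and timing for a CVA of any grade and attribution are stated once. Which timeline to adopt is for the sponsor.

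The cost is a few sentences and one reconciliation. Grade and relatedness are already recorded for every AE under 8.1, so no new data are needed within the existing windows. The downside is that the reported safety figures may look slightly less favourable.

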11.3.3. Analysis Plans for Exploratory Objectives

For the exploratory objectives, descriptive statistics will be used to summarize the levels of anti-tumor response, IFN- γ expressing T cells in peripheral blood, T cell receptor repertoire diversity and clonality, and tumor infiltrating lymphocytes and expression of PD-L1 as determined by immunohistochemistry.

11.3.4. Subgroup Analyses

Subgroup analyses for ORR will be performed on the basis of high versus low tumor mutation burden, high versus low PD-L1 expression on cycle 1 index tumor biopsy, HPV/EBV status, metastatic versus locally recurrent disease, and tobacco smoking history.

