 - PFS is defined as the time from D1 of treatment until the criteria for disease progression is met as defined by RECIST1.1 or death as a result of any cause.
 - OS is defined as time from D1 of treatment until death as a result of any cause.
 - CB will include confirmed complete response (CR) + confirmed partial response (PR) + stable disease at \geq 6 months (SD) and will be determined as per RECIST1.1.
 - Duration of response is the period measured from the time that measurement criteria are met for complete or partial response (whichever status is recorded first) until the date that recurrent or progressive disease is objectively documented.
- Determine the impact of NKTR-214, palliative RT, and anti-PD-1 therapy on patient-reported health-related quality of life (HRQoL)
 - *Outcome measures:* Patient-reported HRQoL will be monitored to evaluate participant tolerance of treatment using EORTC QLQ-C30, EORTC QLQ-H&N35, and EQ-5D. These will be administered at baseline; 7 days after cycle 1 and cycle 2; then every 12 weeks to the end of treatment + once more at 30 days post treatment. HRQoL will be analyzed in pts who received \geq 1 dose of study drug and have \geq 1 HRQoL assessment.

Exploratory Objectives:

- Evaluate each subject's tumor expression of PD-L1 by histology (using anti-PD-L1 clone 22c3 – standard in UW Surgical Pathology) and determine whether this predicts response to NKTR-214, palliative RT, and anti-PD-1 therapy
- Evaluate the immunologic activation induced by NKTR-214, palliative RT, and anti-PD-1 using serologic and flow cytometry immune assays and T cell receptor sequencing
- Evaluate for histological evidence of antitumor activity based on the cellular phenotype of infiltrate

Population:	24 adult patients of any gender, race or ethnicity, age ≥ 18 with Eastern Cooperative Oncology Group (ECOG) Performance Status 0-2 and a biopsy-proven recurrent/metastatic head and neck squamous cell carcinoma who are taking or will be starting anti-PD-1 therapy and have a need for palliative radiation will be eligible for this study.
Phase:	Phase II
Number of Sites:	1

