2.3. Tertiary/Exploratory

Objective	Brief Description/Justification of Outcome Measure	Outcome Measured By	Time Frame
Evaluate each subject's tumor expression of PD-L1 by histology and determine whether this predicts response to NKTR-214, palliative RT, and anti-PD-1 therapy.	PD-L1 expression has been shown to predict response to immunotherapy regimens. If PD-L1 expression correlates with outcome, it could be used in the future to select patients who have greatest benefit from this regimen.	• Expression of PD-L1 by histology	• Baseline • Cycle 2, Day 8
Evaluate the immunologic activation induced by NKTR-214, palliative RT, and anti-PD-1 using serologic and flow cytometry immune assays and T cell receptor sequencing.	Evaluation of the in vivo immune response will help better define the mechanism of action of this combination therapy.	• Levels of IFN- γ expressing and CD122+ T cells in Peripheral Blood Mononuclear Cells (PBMC) • Diversity and clonality of the T cell receptor repertoire by deep sequencing of PBMC	• Cycle 1, 2, and 3, Day 1 prior to treatment infusion • Cycle 1, 2, and 3, Day 8 • 30 days post-treatment
Evaluate for histological evidence of antitumor activity based on the cellular phenotype of infiltrate.	Evaluation of the in vivo immune response will help better define the mechanism of action of this combination therapy.	• Levels of tumor infiltrating lymphocytes by histology	• Baseline • Cycle 2, Day 8

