4. STUDY POPULATION

4.1. Participant Inclusion Criteria

To be eligible to participate in this study, an individual must meet all of the following criteria:

1. Written informed consent and HIPAA authorization for release of personal health information. NOTE: HIPAA authorization may be included in the informed consent or obtained separately
2. Qualify for anti-PD-1 therapy based on current guidelines at the time of registration. This includes the standard requirement for the participant's tumor to have been previously determined to express PD-L1 with a combined positive score ≥ 1 , as determined by an FDA-approved test.
3. Age 18 years and older at the time of consent
4. ECOG Performance Status of 0-2 within 30 days prior to enrollment
5. Histologically proven diagnosis of head and neck squamous cell carcinoma that is metastatic or recurrent disease that is surgically incurable
6. Prior cancer treatment other than anti-PD-1 therapy must be completed at least 30 days prior to registration and the subject must have recovered from all reversible acute toxic effects of the regimen (other than alopecia) to \leq Grade 1 or baseline. Patients may not undergo concurrent anti-cancer treatment during treatment with protocol therapies. This includes no treatment with growth factors, tyrosine kinase inhibitors, tumor-specific antibodies, or cytotoxic chemotherapies such as cisplatin. Patients who have previously or are currently taking an anti-PD-1 therapy are eligible for this study if they meet eligibility criteria 2. Patients who have previously taken any other immune checkpoint inhibitor are eligible as long as they have completed that treatment at least 30 days prior to registration and meet all other eligibility criteria.
7. Subjects with central nervous system (CNS) metastases are eligible if the CNS lesions are stable for at least 2 months and if tapered off treatment doses of systemic corticosteroids for at least 2 weeks prior to enrollment on the trial. Management with maintenance physiologic doses of corticosteroids (equivalent doses of prednisone ≤ 10 mg daily) is acceptable.
8. Subjects must have an "index" tumor that: 1) is deemed by the treating radiation oncologist to potentially benefit from palliative radiation 2) is amenable to biopsy, 3) is ≥ 1 cm in longest dimension.
9. Demonstrate adequate organ function as defined in the table below; all screening labs to be obtained within 30 days prior to enrollment

System	Laboratory Value
Hematological	

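### The only planned link between PD-L1 and response is an ORR comparison of high and low groups with no cut stated; a full-scale analysis would answer the objective better at no extra data cost

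*Combined protocol and SAP*

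**What the plan says.** - **Objective.** The exploratory objective in the Protocol Summary and Section 2.3 is to measure tumor PD-L1 and "determine whether this predicts response to NKTR-214, palliative RT, and anti-PD-1 therapy". Section 2.3 gives the purpose: "If PD-L1 expression correlates with outcome, it could be used in the future to select patients who have greatest benefit from this regimen".
- **Exploratory analysis plan.** Under Section 11.3.3, "descriptive statistics will be used to summarize the levels of anti-tumor response", and the list of summaries ends with "tumor infiltrating lymphocytes and expression of PD-L1 as determined by immunohistochemistry". Nothing there relates PD-L1 to response.
- **Subgroup plan.** Section 11.3.4 states: "Subgroup analyses for ORR will be performed on the basis of high versus low tumor mutation burden, high versus low PD-L1 expression". The PD-L1 part reads in full "high versus low PD-L1 expression on cycle 1 index tumor biopsy". No cut, score, test or alpha is given, and nothing says when the cut is to be fixed.
- **Only PD-L1 threshold in the text.** Inclusion criterion 2 (Section 4.1) requires the tumor to "express PD-L1 with a combined positive score ≥ 1 , as determined by an FDA-approved test". That is an eligibility result obtained earlier, not a rule for this analysis.
- **Tissue.** Sections 6.1 and 7.1.7 provide archival tissue at screening where available. Sections 6.4.2, 7.1.8 and 7.2.2 and Appendix A schedule the index tumor biopsy at cycle 2 day 8. No index biopsy is scheduled in cycle 1.

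**The concern.** The objective asks about prediction. The one analysis that addresses it reduces PD-L1 to two groups and leaves the boundary open. Two things follow.

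First, if the score is graded, a split ignores differences within each group. With at most 24 patients and perhaps 5 to 11 responders (24 × 0.22 = 5.3; 24 × 0.44 = 10.6), little information can be spared.

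Second, this is a single-arm trial with investigator-assessed response, so outcomes are known to the team as they accrue. A cut chosen at that stage can make PD-L1 look predictive when it is not. Because the stated use is future patient selection, either error could mislead the design of a later trial. Tumor mutation burden is handled the same way, and no assay for it is described.

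**Working it through.** The plan gives no power, alpha or effect size for this analysis, so there is no stated figure to reproduce. What follows is illustration.

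**Inputs from the documents:** n = 24; ORR 22% (null) and 44% (target), Section 11.2.

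**Assumptions:** standard normal score x; log-linear effect with odds ratio (OR) 2 to 4 per SD; split at the sample median (12 and 12); two-sided 5%; an intermediate ORR of 33%.

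**Model:** logit P(response) = a + ln(OR) × x, with a set so that the average response equals the chosen ORR. Each simulated trial is tested three ways:
- Pearson chi-square on the 2 × 2 table, n(ad − bc)² / [(a+b)(c+d)(a+c)(b+d)];
- Fisher's exact test on the same table;
- the exact Wilcoxon rank test of the full score, responders against non-responders.

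| ORR | OR per SD | Split, chi-square | Split, Fisher | Rank test | Loss against chi-square |
|---|---|---|---|---|---|
| 44% | 2 | 26% | 15% | 30% | 4 points |
| 44% | 3 | 47% | 31% | 57% | 10 points |
| 44% | 4 | 61% | 44% | 74% | 13 points |
| 33% | 3 | 39% | 24% | 52% | 13 points |
| 22% | 3 | 29% | 16% | 42% | 13 points |

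Over OR 2, 3, 4 and ORR 22%, 33%, 44%, the chi-square loss is roughly 3 to 18 points. It is smallest at OR 2 with ORR 44% and largest at OR 4 with ORR 22%. Repeat runs differ by about a point.

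**Why chi-square is the fairer comparator.** With no association and ORR 44%, rejection rates are about 2% (Fisher), 6% (chi-square) and 5% (rank test). One table shows the gap. Take 11 responders, 8 of 12 high and 3 of 12 low. Chi-square is 24 × (8×9 − 4×3)² / (12×12×11×13) = 86,400 / 20,592 = 4.20, p = 0.04. Fisher's two-sided p is 2 × 124,224 / 2,496,144 = 0.10. Part of the larger loss against Fisher is therefore that test's conservatism, not the split.

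**Cut chosen after seeing responses.** With no association, take the smallest p over all cuts leaving at least 5 patients on each side. The nominal 5% error becomes about 12-16% (Fisher) or 26-29% (chi-square) for ORR 22% to 44%. This needs no assumed effect size.

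**Fewer usable samples.** With 18 scored patients (assumed), OR 1.5 to 4 and a score test on the full scale, the median-split loss against chi-square is about 3 to 22 points.

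**If PD-L1 acts as a threshold.** Let ORR be 22% below and 66% above a threshold at the middle of the distribution (overall 44%). A chi-square test split at that threshold has about 61% power and a sample-median split about 49%, against about 43% for the rank test. The ordering reverses.

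**The case against.** The strongest reply is that Section 11.3.4 plans ORR by subgroup for an exploratory aim and Section 11.3.3 is descriptive. No test or alpha is stated, so power and false-positive rates belong to tests supplied here, not to the plan. That stands, and it is why every figure above is conditional.

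Three further points also stand:
- The analysis scale is inferred. The documents name an antibody clone and, for eligibility, a combined positive score; they do not say how PD-L1 will be scored for 11.3.4.
- A full-scale analysis is not well powered either: about 30% at an odds ratio of 2 and 57% at 3, with ORR 44%.
- Under a threshold relation a split at the right place does better, so the full scale is not superior in every case.

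A reader might infer that the plan loses a fixed amount of power, such as 4 to 35 points. The documents do not support that, because effect size, distribution, cut and test are all unstated. Across quartile and median cuts and both tests, the difference from a full-scale score test runs from about −1 to 61 points.

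A reader might also infer that the entry threshold cannot divide enrolled patients. That is too strong, because 11.3.4 refers to a different specimen, which could score below 1.

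None of this removes the gap between an objective about prediction and an analysis with an undefined split.

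**Conclusion.** The concern holds in limited form. The only planned PD-L1-by-response analysis uses an unspecified high/low split, and a full-scale analysis would serve the stated objective better if the score is graded and its relation to response is smooth. Under those assumptions the loss is roughly 3 to 18 points of power against chi-square with 24 patients. The open cut is the more robust part of the point, since its possible inflation does not depend on an effect size, but it arises only if a test is run at a cut picked from the responses. The plan does not say that this will be done, and it would be wrong to read 12-29% as the plan's error rate.

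The specimen named in 11.3.4 is absent from the schedule, so the number with a usable score may be below 24. The result is hypothesis-generating under any method. This is a desirable refinement; the primary ORR analysis is unaffected.

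**What to change.** In Sections 11.3.3 and 11.3.4:
1. Name the specimen and the PD-L1 score. Reconcile the cycle 1 index biopsy with the schedule, and report the number of patients with a usable score. A cycle 2 day 8 sample is taken after treatment has begun, so it cannot stand in for a pre-treatment predictor without saying so.
2. State the analysis for the PD-L1 objective in 2.3: PD-L1 on its full scale (and tumor mutation burden, if measured) against confirmed response. Use either a rank-based comparison with AUC and 95% CI, or Firth or exact logistic regression with a transform that allows scores of zero.
3. Keep the high/low ORR table at one cut, fixed and dated before response data are reviewed. This also covers the case of a threshold effect, where the rank test has less power.
4. Label the results hypothesis-generating.

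The cost is a few sentences of analysis text and one decision on the specimen. The change of method itself needs no new data. The logistic option assumes a monotone relation on the transformed scale; the rank method needs no linearity assumption.
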